and slowly titrated up to maintenance dose. Gabapentin has been used successfully to treat neuropathic pain and perioperative pain ¹³. It has been shown to reduce stroke size, decrease the cortical spreading depression (CSD), which in turn can cause vasospasm and delayed ischemic neurologic deficit (DIND) ¹⁴. Mayo Clinic Jacksonville has been using gabapentin in order to reduce the narcotic requirement and complication. In our retrospective chart review in neurocritical care ICU (NICU) from January 2011 till February 2013, study (53 patients) there was 6% nausea (intolerable in 1.9%) but no major adverse effects of gabapentin maintenance dose (1800-2700mg /day). We also found a decrease in mean use of opioids with the use of gabapentin within the first 4 days post SAH compared to after 5 days (P = 0.01) . There was no fall, dizziness and abnormal liver function associated with the use of gabapentin. Aseptic meningitis was detected with the analysis of cerebrospinal fluid (CSF) during the second half of the ICU stay. The cost of 300mg of gabapentin was average of 30 times less than intravenous fentanyl 100 mcg. We did not find any other study looking at the use of gabapentin in aSAH patients.

The plan is to conduct a randomized control trial with a total of 20 aSAH patients. 10 aSAH patients admitted in NICU will be assigned to receive gabapentin, and 10 will receive placebo. Both of the groups will receive standard of care for pain control for 7 days.

Hypothesis: “Gabapentin will reduce the pain score and narcotics requirement_among hospitalized aSAH patients compared to placebo alone.”

The primary specific aims and hypothesis of this study are:

1. To compare the narcotic requirements among SAH patients experiencing headache treated with gabapentin or placebo for 7 days.
2. To compare efficacy of gabapentin in reducing the headache numeric pain score (NPS) compared to the non-GBP arm among hospitalized aSAH patients. Both groups are treated by an existing standard of care algorithm with narcotics and NSAIDs.

The secondary aims of this study are:

1. To evaluate the initial dose, escalation and side effects of gabapentin (nausea, vomiting, fall, lightheadedness, dizziness, vertigo, confusion).
2. To evaluate the incidence of delirium, vasospasm, delayed ischemic neurologic deficit (DIND) and seizure among hospitalized aSAH patients.
3. To evaluate the incidence of aseptic meningitis with cerebrospinal fluid (white blood cell and red blood cell ratio).

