C.1.a. Subarachnoid Research: Mayo Clinic Florida (MCF) is a high-volume SAH referral center with an average of about 90 SAH patients a year making this an ideal study population and site to conduct the research study. MCF has a prospective cerebrovascular database of SAH patients that is kept by 3 full-time Neuroscience research coordinators. MCF would be an ideal place to start the GBP study since our center has an existing IRB approval and retrospective study that has shown safety and tolerability of this agent as part of standard management (IRB 13-003673)⁴¹. The purpose of this study is to provide more prospective scientific study to see if the results fit the retrospective data, and possibly help with a larger extra-murally funded trial examining this drug. MCF has a team of experienced neurologists, and intensivists, as well as research coordinator in order to conduct this project. Other trials conducted at MCF in the NeuroICU include CLEAR3 (NCT00784134), ATACH2 (NCT01176565) that are NIH/NINDS funded national/international trials. [name] as the mentor of this study has extensive clinical experience in SAH patients, and has significant research experience in SAH and neurocritical care. He has served as site principal investigator of the aforementioned multicenter research trials at MCF, and is a productive mentor with mentees being academically productive with research abstracts and full-length publications. [name] also holds a FDA-investigational new drug (IND) for nicardipine for SAH, and has experience with this process with the FDA. Similarly [name] has been involved in multiple NIH/NINDS. He have received CREST-2, The National Institute of Neurological Disorders and Stroke which will begin enrolling 2,480 patients in 120 centers in the United States and Canada with carotid disease.

C.1.b. Gabapentin for headache in SAH Research: Our research group at MCF conducted a retrospective study of a consecutive series of SAH patient from January 2011 till February of 2013 in the neurointensive care unit⁴¹. The study had 53 aSAH patients who were treated with GBP along with standard of care analgesics, NSAIDs and sometimes dexamethasone for severe headache. Severe headache was observed in all aSAH patients, with average maximal

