intensity on day 5 of aSAH. GBP dosing was rapidly escalated within days of SAH up to a median of 1200 mg/day, with a range of 300 mg three times a day to 900 mg three times a day which was overall well-tolerated. Approximately 6% of patients treated with GBP had nausea (95% CI, 1-16%) that is also associated with SAH disease. Only 1 patient (1.8%) had to discontinue GBP due to nausea and vomiting. GBP dose was rapidly weaned similar to its tiered dose escalation or stopped after discharge in most of the patients. There were no major reported GBP withdrawal side effects such as seizure. However approximately, 4 patients had return of headaches observed after they weaned off the medication within a 30 day period in which case, GBP was resumed until headaches resolved. In 2 of these cases GBP was used for their outpatient management of baseline migraines or postoperative craniotomy headaches. In the Mayo Clinic study, visual analog scale (VAS) was used which is similar to NPS and was charted on a daily basis to document pain severity. VAS in these patients showed a slow rise from day one of aSAH until a maximum intensity around day 5. Two different peaks on day 11 and day 16 after aSAH were also noted subsequently. These peaks in VAS score also interestingly correlated with high CSF WBC/ RBC ratio and there were no culture proven bacterial or viral infection. This data suggests the inflammatory delayed headache pathophysiology of SAH headache and separate from the initial headache onset. These headaches also were more responsive to corticosteroids apparently since steroid use for breakthrough pain was noted during this time period. This data provides important insight that this period of time of post-SAH headache and meningismus may be a form of inflammatory or steroid- responsive aseptic meningitis.

Overall, the Mayo Clinic study demonstrated that GBP is safe and tolerable in aSAH patients with headache. No major adverse events (AE) were noted. A small portion of patients reported nausea that is inherent to SAH disease, and was managed conservatively with typical anti-nausea medications and did not require GBP discontinuation. The escalation of GBP in this population also appeared feasible and without major side effects. We saw decrease trends in use of opioid and steroids requirements with upward titrated and therapeutic doses of GBP.

C.2. Current Proposal Overview

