This study will be a randomized, placebo-controlled clinical trial enrolling 20 subjects at MCF to either GBP + standard of care (SOC) vs placebo + SOC arm. While enrolling the patients we will stratify patients via numerical pain score (NPS) to either <5 or ≥ 5 . Patients with an NPS ≥ 5 will be randomly assigned to either GBP or placebo group within 72 hours of SAH admission and after informed consent. The SOC pain regimen is comprised of intravenous (IV) fentanyl 25mcg to 50mcg q1hr PRN for head and neck pain as the first-line agent. If SAH pain remains >5 on NPS after the next nursing pain assessment, the next tier of pain agents will be utilized consisting of the following tier:

2nd line- enteral /PO oxycodone 5mg PRN q4hrs pain, and if still in pain after next assessment, then 10mg q4hrs PRN,

3rd line (if 2nd line failed to reduce NPS < 5)- IV 15mg ketorolac q6hrs PRN x 24hrs, unless serum creatinine > 1.3 , or GFR < 30 , or concern for gastrointestinal bleed risk, or history of bleeding peptic ulcer.

4th line (if 3rd line failed to reduce NPS < 5)- dexamethasone 2mg IV BID x 24hrs.

The patient will be enrolled within 72 hours of admission and meeting inclusion criteria by investigator and coinvestigators. Documentation of numeric pain score will be done by standard of care per nursing and hospital policies in the medical record. After consent and enrollment, a data collection sheet will be recorded by nursing to summate the NPS scores every 24 hours along with the SOC pain management plan. The SOC pain management plan will be implemented by the NeuroICU team of residents, attending, and nurse practitioners/PA's who are available on a 24/7 basis. A decrease in pain score equal or more than 50% will be defined as meeting the goal of the study, and as headache pain being under control. Patients will begin study medication (gabapentin or placebo) at approximately 9:00 AM on the morning following randomization into the trial to allow for documentation of the baseline average NPS. The

baseline NPS will be used to determine if the patient has had a 50% or more decrease in pain score.

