2. Have aneurysmal SAH diagnosed by CT scan of the brain and/or angiogram evidence of intracranial aneurysm (CTA or digital subtraction angiogram or MRA)
3. Have symptomatic headache
4. Able to swallow and verbalize pain score
5. No known allergy to GBP or fentanyl
6. Numeric pain score \geq 5
7. Ability to provide written personal consent

Exclusion Criteria:

1. GBP use prior to SAH admission
2. Renal failure with creatinine clearance less than 30 ml/min
3. Unable to receive standard of care pain medications
4. Pregnant patients
5. History of severe depression defined by DSM IV

C.4. Study Procedures & Schedule

All study medication will be labeled and dispensed according to subject number ensuring that treatment assignment remains concealed to the subject, investigator, and all study personnel who have subject contact. Data collection will be done in case report form at the bedside and

later will be enter in spread sheet. We will issue unique ID for each study patients. 20 preprinted study ID labels will be used to randomly select study patients.

Subject selection: All aneurysmal SAH admitted will be screened by the Mayo Cerebrovascular laboratory for eligibility and the NeuroICU attending and/or fellow will be contacted about potential enrollment in the study. Subjects who are able to provide written consent will be approached for enrollment. Based on prior volumes, we expect to have 20 subjects enrolled within 6-9 months.

Pain assessment: We will use numeric pain scale (NPS) that is been validated in many studies and is easy to use. Nurse and medical staff are familiar with this scale in our institute as it has been commonly used as standard of care. We plan to perform this pain scale every 4 hours in the study patients. The scale range from 0-10, 0 being the no pain and 10 being the worst pain ever. We will calculate daily total score for each patient. Only headache and neck pain will be included in the study to calculate the pain score. We will not include the score for other pain like back and abdominal pain.

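### Exclusion 1 stops at admission, so patients given gabapentin in hospital before randomisation stay eligible and may enter with a treated baseline

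*Combined protocol and SAP*

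**What the plan says.** **Eligibility.** Exclusion 1 in C.3 reads "GBP use prior to SAH admission". No other criterion, washout or pre-randomisation medication rule mentions gabapentin.

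**Timing.** C.2 states: "The patient will be enrolled within 72 hours of admission". Patients are "randomly assigned to either GBP or placebo group within 72 hours of SAH admission and after informed consent". Study drug starts at about 9:00 AM "on the morning following randomization into the trial to allow for documentation of the baseline average NPS". That baseline is the reference for the 50% reduction. In C.2 and C.5 the 50% reduction also defines the maintenance dose and so governs escalation.

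**Site practice.** Section 2 says: "Mayo Clinic Jacksonville has been using gabapentin in order to reduce the narcotic requirement and complication". C.1.a refers to a "retrospective study that has shown safety and tolerability of this agent as part of standard management". C.1.b describes 53 treated patients and says "GBP dosing was rapidly escalated within days of SAH".

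**Text pointing the other way.** The pain ladder in C.2 consists of fentanyl, oxycodone, ketorolac and dexamethasone, without gabapentin. Section 2 describes the current standard algorithm as opioids and NSAIDs. The abstract defines the comparator as standard care without gabapentin. C.2 mentions gabapentin for placebo patients only after day 7, although it calls that use standard of care.

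**The concern.** Excluding earlier gabapentin users suggests that the trial wants patients who are new to the drug. The cut-off falls at admission, up to 72 hours before randomisation, and this is a site that has used gabapentin for the same headache in the same unit. A patient who received it on hospital day 1 or 2 meets every criterion as written, provided that pain is still at least 5.

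Three things would be affected if such patients were enrolled:

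- **Baseline.** The reference for the 50% goal and for titration would be measured on gabapentin or just after it stopped, in either arm.
- **Placebo arm.** A pre-exposed patient allocated to placebo changes from gabapentin to none. That patient may carry over some benefit or have pain return.
- **Secondary aim 1.** The first study dose would not be a true initial dose, so the description of starting dose, escalation and side effects would mix new and pre-treated patients.

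**Working it through.** The plan gives no figure for exposure before randomisation, so there is none to reproduce. The sizes below are conditional, and the assumptions are named.

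**1. The window.** The exclusion ends at hour 0 (admission). Randomisation may come as late as hour 72, and the first study dose follows the next morning. The retrospective series had gabapentin being escalated within days of the bleed. The two periods can overlap, and no criterion covers the overlap.

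**2. Effect on the 50% goal.** Assume that gabapentin lowers pain by 25%, the difference used in C.7, and that the baseline is taken under the full effect. The target is then 0.50 × (1 − 0.25) = 0.375 of the untreated level, which is a 62.5% fall from untreated pain instead of 50%. If pain has instead risen after gabapentin was stopped, the target is easier to reach. Either applies to pre-exposed patients in both arms.

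**3. Upper bound for dilution.** Let f be the share of the placebo arm that carries the full gabapentin effect for the whole 7 days. The contrast becomes 25% × (1 − f), and the sample size for the same power is multiplied by 1/(1 − f)². With 10 per arm, each such patient adds 10% to f.

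| f | Contrast | Sample-size factor |
|---|---|---|
| 10% | 22.5% | 1/0.81 = 1.23 |
| 20% | 20.0% | 1/0.64 = 1.56 |
| 30% | 17.5% | 1/0.49 = 2.04 |

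**4. The same bound as power.** C.7 gives SD 5.84, alpha 0.05, 80% power and a 25% difference, but not the mean or the scale. I assume the daily total (six readings, range 0 to 60) with a control mean of 30, so the difference is 0.25 × 30 = 7.5. Then n per arm = 2 × [5.84 × (1.960 + 0.842)/7.5]² = 9.5, or 10, close to the plan's claim of fewer than 10. Power at 10 per arm is Φ[d/(5.84 × √(2/10)) − 1.96], where d = 7.5 × (1 − f):

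| f | d | Power, mean 30 | Power, mean 36 |
|---|---|---|---|
| 0 | 7.50 | 82% | 93% |
| 10% | 6.75 | 73% | 87% |
| 20% | 6.00 | 63% | 79% |
| 30% | 5.25 | 52% | 67% |

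The last column assumes a mean of 36 instead (difference 9.0 at f = 0). These are normal approximations. With the t distribution the mean-30 column is 4 to 5 points lower. The unstated scale in C.7 is a separate matter.

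**5. Shorter carry-over.** If the effect lasts k of the 7 days and the outcome is the 7-day average, f is replaced by f × k/7. Taking k = 1 as an assumption, f = 30% gives 1 − 0.30/7 = 0.957, a contrast of 23.9% and a factor of 1/0.957² = 1.09. For f = 10% the factor is 1.03.

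**6. The other direction.** If stopping gabapentin raises a placebo patient's pain by w, the contrast grows by f × w. C.1.b reports about 4 patients whose headache returned after weaning within a 30-day period. It gives no size for w, so the sign of the net effect is not determined.

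**The case against.** The strongest reply is that exposure is never shown. The series ran from January 2011 to February 2013, before this protocol. Section 2 and C.2 describe a standard regimen without gabapentin, and the word used in Section 2 implies that it was already in place before enrolment. This stands. A reader might infer that the baseline and placebo arm will be contaminated, but the documents support only that the criteria allow it.

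Second, exposure before randomisation falls on both arms equally in expectation. The C.6 comparison of pain score, satisfaction and fentanyl states no baseline adjustment, so a treated baseline does not enter that test directly. This also stands for the test. It does not remove the effect on the 50% goal and titration. Nor are the later consequences symmetric, because one arm continues gabapentin and the other stops it.

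Third, the entry threshold of 5 limits how well treated a pre-exposed patient can be. It still admits those whose pain persists on gabapentin.

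Fourth, C.4 already tabulates the gabapentin dose for each hospital day, and C.2 and C.6 already specify intention to treat. That is correct, and neither needs changing. Recording a dose does not make the patient ineligible, however, and no analysis rule covers doses given before randomisation.

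A reader might also infer that placebo patients would receive open-label gabapentin during the 7 days. No explicit prohibition is written, but the comparator and the after-day-7 provision show that this is not intended.

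**Conclusion.** The point holds as an eligibility gap with a conditional consequence. As written, C.3 admits patients given gabapentin between admission and randomisation, at a site whose own account makes such use plausible. If any are enrolled, their baseline does not represent untreated pain, and those on placebo may show carry-over or withdrawal.

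The number exposed is unknown, and the effect on the between-arm contrast could go either way. The factors 1.23, 1.56 and 2.04 should not be read as expected inflation. They are upper bounds on dilution, and they assume that 10%, 20% or 30% of placebo patients keep the full effect for all 7 days. Exposure limited to the days before randomisation gives no basis in the documents for that persistence. What is certain is the leverage: one such patient is 10% of the placebo arm. This is a cheap improvement and not a flaw that invalidates the design.

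**What to change.** Reword exclusion 1 in C.3 to: *any gabapentin use before randomisation, including since this admission*. Reconcile Section 2, C.1.a and C.2 on whether gabapentin is part of standard care at the site, since they currently point in different directions.

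The text change is one line plus the reconciliation. The cost is accrual, because patients already started on gabapentin become ineligible. If a share s of otherwise eligible patients is lost, the planned 6 to 9 months becomes 6/(1 − s) to 9/(1 − s): about 6.7 to 10 months at s = 10%, and 8.6 to 12.9 months at s = 30%. These shares are assumptions. If exposure is rare the cost is small; if it is common the cost rises, but so does the need for the rule. The site sees about 90 subarachnoid haemorrhage patients a year and needs 20, which leaves some room.

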4. To evaluate the pain control satisfaction among patients treated with or without gabapentin.

If gabapentin reduces the pain and/or improves pain control satisfaction without major side effects it will be drug of choice for headache among patients with SAH with lower cost benefit ratio by decreasing the narcotic requirement.

3. Research Strategy a. Significance

A.1. Subarachnoid hemorrhage

Subarachnoid hemorrhage is mainly due to rupture of saccular aneurysm. This is often a devastating clinical event with mortality rates that approach 40 percent by one month, as well as substantial neurologic morbidity in SAH survivors. The lifetime cost per person of first strokes occurring in 1990 is estimated to be \$228,030 for SAH. Indirect costs accounted for 58.0% of lifetime costs. Aggregate lifetime cost associated with SAH is estimated to be about \$5.6 billion in the U.S. Acute-care costs incurred in the 2 years following a first stroke accounted for 45.0% of these costs, while long-term ambulatory care accounted for 35.0%, and nursing home costs

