Narcotic Requirement: We will use intravenous fentanyl as a pain medication. The dose range of fentanyl will be from 25 micrograms to 50 micrograms, which could be repeated hourly. Total daily requirement of fentanyl for head and neck pain will be calculated every day. The side effects of the fentanyl will be prospectively charted. We plan to use subsequent line of pain management as describe in the text above if not controlled by fentanyl or have side effects with it.

Laboratory variables: Whenever cerebrospinal fluid (CSF) is collected by standard of care via an external ventricular drain or lumbar specimen. We will review this data for white blood cell (WBC), red blood cell (RBC) counts, as well as the CSF WBC/RBC ratio and culture and sensitivity. We will also review values of kidney function (creatinine and BUN), in the medical record performed as standard of care by the treating team.

Radiological variables: We will review patient CT or CT angiography done by standard of care by the treating team. We plan to get SAH severity using the Fisher grade, aneurysm location, follow up CT angiography and/ or transcranial Doppler for detection of vasospasm.

Aseptic Meningitis Screening: In order to screen that meningitic pain after aSAH was not due to from frank bacterial (septic) meningitis, CSF data will be reviewed from existing external ventricular drain (EVD) or CSF samples especially when there is fever and headaches documented in the electronic health record. The CSF culture result will also be analyzed to rule out any bacterial meningitis or ventriculitis. When CSF WBC is elevated and culture is negative for microorganisms, with persisting headache, these groups will be defined as 'aseptic' or inflammatory meningitis. Any patient who develops bacterial meningitis will be excluded from final headache analysis since the pathology will be different. The incidence of bacterial meningitis in SAH patients with EVD is < 1.0% and unlikely given the small sample size of this study. Also GBP medication is not expected to in any way increase the risk of bacterial meningitis based on our retrospective study and existing FDA safety data on GBP.

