Gabapentin escalation dosing will be modeled after our retrospective safety study. We will start with 100 mg orally three times a day then every 24 hours increase to 300 mg tid as tolerated, then 600 mg tid and to a maximum of 900 mg tid. We plan to use 100mg tid then 200 mg tid and 400mg tid if creatinine clearance of 30 -59. We will exclude any patients who have CrCl <30. We will define maintenance dose of GBP as a dose in which after being on it for 24 hours there is 50% reduction of daily average NPS. We will continue maintenance dose throughout hospital stay. aSAH patients will be in observation in NICU for median of 15 days. The placebo will be escalated in the same manner as GBP. A Mayo pharmacist would dispense the study drug (ie., GBP or placebo). Every patients discharged with aSAH will be followed by Mayo neurologist as a SOC and they will plan to reduce or stop GBP.

C.6. Data Analysis

Unless otherwise specified, analyses will be performed using an intention-to-treat approach whereby subjects are analyzed according to randomized treatment arm. The primary endpoint for this trial will be the 7 days of treatment with or without GBP and best medical therapy. For this endpoint the treatment groups will be compared using a two-tailed test with a p -value ≤ 0.05 .

Categorical variables will be summarized as percentages, and continuous factors will be described using means or medians to best describe the distributions. Adverse events will be described as rates, and 95% confidence intervals estimated for those rates. The calculated total daily NPS score; opioid requirement and GBP dose will be analyzed. CSF WBC/RBC ratio will be calculated from the available sample and trended on days of SAH. All the plotted data will be projected with a 95% confidence interval.

We will compare the NPS, patient satisfaction score and the fentanyl requirement among the GBP and placebo group. We will use 2 sample t test or Wilcoxon rank sum test. The data will be analyzed to see if there is difference in incidence of aseptic meningitis, vasospasm and DIND between the GBP and placebo group. If there is difference more than 5 %, we will use regression modeling to analyze the data.

C.7. Sample Size Considerations

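### Primary aim 1 is the narcotic requirement, but the plan totals and compares only fentanyl and leaves oxycodone, the ladder's second opioid, outside the endpoint

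*Combined protocol and SAP*

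**What the plan says.** Section 2 gives the first primary aim as "To compare the narcotic requirements among SAH patients experiencing headache treated with gabapentin or placebo for 7 days". It goes on to say that a favorable result would make gabapentin the "drug of choice for headache among patients with SAH with lower cost benefit ratio by decreasing the narcotic requirement".

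The standard-of-care ladder in C.2 starts with IV fentanyl 25–50 mcg hourly as needed. The next tier is "2nd line- enteral /PO oxycodone 5mg PRN q4hrs pain, and if still in pain after next assessment, then 10mg q4hrs PRN". Ketorolac and dexamethasone follow; neither is an opioid. C.4 says the team will move to the "subsequent line of pain management as describe in the text above if not controlled by fentanyl or have side effects with it".

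Three places bear on how the narcotic requirement is measured:

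- C.4, Narcotic Requirement: "Total daily requirement of fentanyl for head and neck pain will be calculated every day". The later lines appear in this paragraph only as treatments that may be given. No total is derived for them.
- C.6, between-arm comparison: "We will compare the NPS, patient satisfaction score and the fentanyl requirement among the GBP and placebo group".
- C.6, list of variables: "opioid requirement and GBP dose will be analyzed". No definition is attached.

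On data capture, C.2 says "a data collection sheet will be recorded by nursing to summate the NPS scores every 24 hours along with the SOC pain management plan". It does not list oxycodone doses as an item on that sheet.

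**The concern.** Narcotic, fentanyl and opioid are used for the same aim and are never reconciled. The only total that is defined, and the only narcotic variable named for comparison between arms, covers the first of two opioids.

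The omission is not neutral, because oxycodone is started in response to what happens after randomization: pain that fentanyl does not control, or fentanyl side effects. The trial's hypothesis is that gabapentin reduces pain, so the unmeasured part of the endpoint may differ by arm.

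Oxycodone use is also not a remote possibility under the plan's own rules. Entry requires a pain score of at least 5, step-up follows if the score is still above 5 at the next nursing assessment, and assessments are every 4 hours. Participants must be able to swallow and to receive the standard-of-care medications.

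At stake is the answer to a primary aim. Leaving the term open would also allow the choice between fentanyl and total opioid, and the choice of conversion, to be made after results are seen.

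**Working it through.** The plan gives no effect size, SD or expected use for any narcotic measure. The sample-size reasoning in C.7 concerns the pain and satisfaction scores, so there is no narcotic figure to reproduce. The check is a comparison of passages, followed by arithmetic for scale.

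**Is oxycodone in the endpoint?**

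| Place | Term | Drugs covered |
|---|---|---|
| Section 2, aim 1 | narcotic | not listed |
| C.2 ladder | – | fentanyl, then oxycodone |
| C.4 Narcotic Requirement | fentanyl total | fentanyl |
| C.6 between-arm comparison | fentanyl requirement | fentanyl |
| C.6 variable list | opioid requirement | not listed |

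No section defines an oxycodone total or a combined opioid measure.

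**Ladder maxima (doses from C.2)**

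- Fentanyl: 50 mcg × 24 = 1,200 mcg/day.
- Oxycodone, 10 mg step: 10 × 6 = 60 mg/day. At the 5 mg step: 5 × 6 = 30 mg/day.

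**Conversion.** The documents give none. Assume r mcg IV fentanyl per mg oxycodone, with r = 3 to 10.

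- 60 mg/day: 60 × 3 = 180 to 60 × 10 = 600 mcg/day. As a share of the fentanyl maximum: 180/1,200 = 15% to 600/1,200 = 50%.
- 30 mg/day: 90 to 300 mcg/day, or 7.5% to 25%.
- Seven days at the maximum: 60 × 7 = 420 mg, or 1,260 to 4,200 mcg, against 1,200 × 7 = 8,400 mcg fentanyl.

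**Effect on the comparison between arms.** With every difference taken as gabapentin minus placebo:

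total-opioid difference = fentanyl difference + r × (oxycodone difference)

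The fentanyl-only result is therefore off by r times the arm difference in mean oxycodone.

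- A 10 mg/day oxycodone difference shifts the result by 10 × 3 = 30 to 10 × 10 = 100 mcg/day.
- A 100 mcg/day fentanyl difference is cancelled by an opposing oxycodone difference of 100/10 = 10 mg/day to 100/3 = 33.3 mg/day.
- With 10 patients per arm, one patient on 60 mg/day moves an arm mean by 60/10 = 6 mg/day, or 18 to 60 mcg/day.

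**Can the sign change?** Take hypothetical arm means of 500 mcg/day fentanyl and no oxycodone on gabapentin, and 400 mcg/day fentanyl plus 30 mg/day oxycodone on placebo. Fentanyl alone is 100 mcg/day higher on gabapentin. The total-opioid difference is 100 − 30r: +10 at r = 3 and −200 at r = 10, crossing zero at r = 3.33. Reversal is possible but depends on the conversion.

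**The case against.** The strongest reply is that oxycodone is not clearly excluded. An opioid requirement is listed for analysis, its ordinary meaning covers oxycodone, and the nursing sheet may record the doses. On that view this is loose terminology in a small single-center study whose sample size does not rest on the narcotic endpoint. The part about data collection stands: oxycodone is missing from the defined measure, not necessarily from the records. But an undefined term does not tell the analyst which drugs to add or how, and the comparison that is spelled out names fentanyl.

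The second objection concerns magnitude, and much of it stands. The conversion range is assumed; at 20 mcg per mg the omitted maximum would equal the whole fentanyl maximum (60 × 20 = 1,200). Both maxima assume every permitted dose is given. The documents do not say whether as-needed fentanyl continues once oxycodone starts, nor whether oxycodone continues once later lines begin. A share of the fentanyl maximum is easiest to interpret if the two are given together. The percentages show scale and do not estimate bias.

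Third, if gabapentin improves pain control, fewer gabapentin patients should step up, so fentanyl alone would understate or hide a benefit. Mimicking one requires more oxycodone on gabapentin. That is the less expected direction, but differential fentanyl intolerance or chance imbalance with 10 per arm could produce it.

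Finally, fentanyl and oxycodone could be reported separately without any conversion. That is a sound supplement, but it leaves two results for one aim and no rule for combining them.

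**Conclusion.** The concern holds. Followed as written, the plan answers a primary aim about narcotics with the first-line drug only, and nothing in C.6 brings the second opioid in. The fentanyl total is an incomplete measure of the narcotic requirement, and the missing part depends on post-randomization pain control and tolerance, so the comparison may be biased.

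The direction and size of any bias cannot be determined from the documents. The illustrative figures rest on the assumed 3–10 mcg per mg, on ladder maxima, and on hypothetical arm differences. The finding itself rests on none of these. It should be fixed before the data are analyzed, and preferably before enrollment, because oxycodone doses or pain sites that are not recorded at the bedside may not be recoverable later.

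**What to change.** - Define the aim 1 endpoint as total opioid given for head and neck pain over study days 1–7: fentanyl, oxycodone and any other opioid, converted with one prespecified equivalence table. State the 7-day summary used in the test.
- Name this total in the C.6 between-arm comparison, and use the same term in section 2, C.4 and C.6.
- Keep fentanyl alone as a supportive summary, and show oxycodone separately beside it.
- Keep the head-and-neck scope for the main total, and report opioid for all indications as a sensitivity analysis.
- Repeat the comparison with alternative conversion factors, for example 3 and 10 mcg per mg.
- Confirm that the bedside sheet records each oxycodone dose and the pain site it was given for, and add a field if it does not.

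The cost is SAP wording, one conversion table, a form check and perhaps one added field. The drawback is that the combined total depends on the conversion chosen, which the sensitivity analysis makes visible. No change to analgesic treatment is proposed.
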